5 STUDY PROCEDURES

5.A Screening/Baseline Evaluations

Unless otherwise specified, the following evaluations must be performed within 28 days prior to C1, D1:

5.A.1 Medical history, including documentation of all prior lymphoma treatments and documentation of the rationale for treatment of the patient's lymphoma with Zevalin

- 5.A.2 Physical examination, including vital signs (BP, temperature & pulse), height, weight, Body Surface Area (BSA) & performance status (Appendix B).
- 5.A.3 Disease Assessment
 - Total of all measurable indicator lesions
 - CT or PET scan of the chest, abdomen and pelvis is recommended for baseline response evaluation.
- 5.A.4 Laboratory tests including:
 - Complete blood count (CBC) with differential and platelet count
 - Serum chemistries BUN, creatinine, total bilirubin, alkaline phosphatase, LDH, SGOT (AST), SGPT (ALT)
 - Serum beta-2-microglobulin
 - Pregnancy test (serum) for women of childbearing potential
 - Hepatitis B screen (encouraged by Good Medical Practice, but not required)
- 5.A.5 Unilateral or Bi-lateral bone marrow biopsy and aspirate for histology and determination of percent bone marrow involvement
- 5.A.6 Bone marrow cytogenetics (Results are not required prior to enrollment). This can also be done with the repeat Bone Marrow biopsy and aspirate at Cycle 2, Day 29. This does not have to be done at each Bone Marrow biopsy and aspirate, but does need to be completed at either, Baseline or Cycle 2, Day 29.
- 5.A.7 Pathology Review: All patients registered on this study are encouraged to undergo pathology review. The purpose of this review is to verify the histologic diagnosis of an indolent non-Hodgkin lymphoma and that the patients are CD20 positive. Any excess tissue will be retained by the Arizona Cancer Center (unless the patient denies consent).
 - a Pathology materials are to be submitted to:

[name].
Department of Pathology
The University of Arizona Cancer Center
[name]
[name]

[contact]

b The following materials would constitute best available material for review:

- Representative H&E stained slides form the diagnostic biopsy. (Note: Needle aspirates are not adequate for this submission. Consult [name] if adequacy of the specimen is in question.)
- One representative paraffin block which will be conserved (no more than eight additional slides will be cut).
- One copy of the pathology report.

5.B Evaluations During ESHAP Treatment Period

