The above mentioned tests and assessment are to be performed within 28 days of Rituximab & Zevalin administration.

d. Rituxaimab Infusion (250 mg/m²) & ¹¹¹In Zevalin (Ibritumomab Tiuxetan Indium) infusion. (Please refer to section 7.B for detailed treatment administration)

5.C.2 Days 2, 3, 4 and 5

a. Gamma Scan: A scan is to be performed at 48-72 hours after ¹¹¹In Zevalin (Ibritumomab Tiuxetan Indium) infusion. Another optional scan may be performed at 90-120 hours after ¹¹¹In Zevalin (Ibritumomab Tiuxetan Indium) infusion.

CAUTION WILL BE TAKEN IN THE HANDLING OF ALL RADIOACTIVE SAMPLES ACCORDING TO STANDARD PROCEDURES AND PRACTICES AT THE CLINICAL SITE

The purpose of ¹¹¹In Zevalin (Ibritumomab Tiuxetan Indium) imaging is twofold:

- To evaluate biodistribution of whole body gamma camera images
- To assess whether biodistribution is acceptable to proceed with ⁹⁰Y Zevalin (Ibritumomab Tiuxetan Ytrium-90) radioimmunotherapy.

The biodistribution of ¹¹¹In Zevalin (Ibritumomab Tiuxetan Indium) should be assessed by a visual evaluation of whole body planar view anterior and posterior gamma images. A set of images at 48-72 hours after injection is required. To resolve ambiguities, optional images at other time points may be necessary. Images should be acquired using a large field of view gamma camera quipped with a medium energy collimator. Whole body anterior/posterior planar images should be acquired using a large field-of-view gamma camera and medium energy collimators. Suggested gamma camera settings: 256 x 1024 matrix; dual energy photopeaks set at 172 and 247 keV; 15% symmetric window; scan speed of 10 cm/min for the 48-72 hour scan, and 7-10 cm/min for subsequent scans.

> Expected biodistribution:

- Activity in the blood pool areas (heart, abdomen, neck, and extremities) may be faintly visible.
- Moderately high to high uptake in normal liver and spleen.
- Moderately low or very low uptake in normal kidneys, urinary bladder, and normal (uninvolved) bowel.
- Non-fixed areas within the bowel lumen that change position with time; delayed imaging as described above may be necessary to confirm gastrointestinal clearance.

Tumor uptake may be visualized in soft tissue as areas of increased intensity, and tumor-bearing areas in normal organs may be seen as areas of increased or decreased intensity. Tumor visualization on the ¹¹¹In Zevalin (Ibritumomab Tiuxetan Indium) scan is not required for ⁹⁰Y Zevalin (Ibritumomab Tiuxetan Ytrium-90) therapy.

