7 TREATMENT PLAN

All patients who qualify for this study will receive chemotherapy with ESHAP followed by treatment with Zevalin

7.A ESHAP REGIMEN DOSING

ESHAP chemotherapy: Patients will receive 2 cycles of cytoreductive chemotherapy according to the schedule described below. (Table 7)

TABLE 7 ESHAP CHEMOTHERAPY PLUS ZEVALIN

DRUG	DOSE	ROUTE	DAYS	INTERVAL
Etoposide	$40 \text{ mg/m}^{2/} \text{day}$	IV infusion over 1 hour	1,2,3,4	q 28 days for 2 cycles
Methylprednisolone	250 mg/day	IV push	1,2,3,4	q 28 days for 2 cycles
		_		
Cytarabine	2000 mg/m^2	IV infusion over 2 hours	4	q 28 days for 2 cycles
Cisplatin	25 mg/m ² /day	IV infusion at 1mg/min	1,2,3,4	q 28 days for 2 cycles

- The cycle length will be 28 days if bone marrow recovery allows. If recovery requires an additional week, then the second cycle will be postponed for a week.
- Either pegfilgastrim or filgastrim may be given at the investigator's discretion.

7.B RITUXIMAB, 111 IN ZEVALIN, AND 90 Y ZEVALIN ADMINISTRATION

The rituximab + ibritumomab tiuxetan regimen is given 4-6 weeks after completion of the second cycle of ESHAP. Treatment can be completed within 7 - 9 days in an outpatient setting

TABLE 8
Rituximab, 111In Zevalin, AND 90Y Zevalin Administration

AGENT	DOSE	ROUTE	DAYS	NOTES
Rituximab	250 mg/m ²	Slow IV	1, then 7, 8 or 9	Give prior to 111 In Zevalin
¹¹¹ In Zevalin	5 mCi	Slow IV push over 10 minutes	1	Give within 4 hours after rituximab
⁹⁰ Y Zevalin	Depends on platelet count (see Section 7.B.3)	Slow IV push over 10 minutes	7, 8, or 9	Give within 4 hours after rituximab

7.B.1 Rituxan & 111 In Zevalin Administration

1.6 mg of ¹¹¹In Zevalin (5.0 mCi of ¹¹¹In) will be used for radioimaging. The imaging dose of ¹¹¹In Zevalin will be administered by a 10-minute slow IV push injection immediately following the infusion of Rituxan. ¹¹¹In Zevalin may be directly injected by stopping the flow from the IV bag and injecting the radiolabeled antibody directly into the line. A 0.22 micron filter must be on line between the patient and the infusion port. Flush the line with at least 10 mL of normal saline after ¹¹¹In Zevalin has been injected. (See Appendix H).

a. Oral premedication (2 tablets [325 mg] of acetaminophen and 50 - 100 mg oral diphenhydramine hydrochloride) may be administered 30 - 60 minutes prior to starting each infusion of rituximab.

7.B.2 Radioimaging Schedule

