Appropriate medical therapy should be provided for patients who develop tumor lysis syndrome. Following treatment for and resolution of tumor lysis syndrome, subsequent

rituximab therapy may be administered in conjunction with prophylactic therapy for this syndrome. Contact the Study Coordinator prior to resuming treatment in these patients.

TABLE 10
Rituximab Infusion rate Adjustment

Fever	Rigors	Mucosal Congestion/ Edema	% Drop in Systolic BP	Infusion Rate Adjustment
Grade 1	Grade 1-2	Grade 1-2	30 – 49	Decrease By 50%
Grade ≥ 2	Grade ≥ 3	Grade ≥ 3	≥ 50%	Stop infusion*

^{*}Temporarily discontinue infusion until adverse experiences have reversed (generally 15 to 30 minutes) and then resume infusion at 25 - 50% of initial rate.

8.B.5 Hepatitis B Reactivation with Related Fulminant Hepatitis and Other Viral Infections: Carriers of hepatitis B should be closely monitored for clinical and laboratory signs of active HBV infection and for signs of hepatitis throughout their study participation. Patients with any evidence of active hepatic disease or known HBV infection should be managed as clinically appropriate and should only receive rituximab if they have control of the infection and are adequately informed of the risks. Patients who have never received vaccination for HBV, and have not had serologic testing for HBsAg, should be tested for surface antigen positivity.

In patients who develop progressive multifocal leukoencephalopathy (PML), rituximab should be discontinued and reductions or discontinuation of concomitant immunosuppressive therapy and appropriate treatment, including antiviral therapy, should be considered. Physicians should consider PML in any patients presenting with new onset neurologic manifestations, particularly in patients with systemic lupus erythematosis (SLE) or lymphoid malignancies. Consultation with a neurologist, brain MRI, and lumbar puncture should be considered as clinically indicated. There are no known interventions that can reliably prevent PML or adequately treat PML if it occurs.

8.B.6 Severe mucocutaneous reactions:

All patients on or off rituximab therapy should be closely monitored for signs and symptoms suggestive of severe cutaneous and mucocutaneous reactions. Should these symptoms arise, discontinue rituximab therapy (if applicable) and support as clinically indicated.

8.B.7 Cardiovascular events:

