13 STUDY ADMINISTRATION

13.A Review and Consent Requirements

13.A.1 Institutional Review Board (IRB)

The investigator will supply all necessary documents to be submitted to the IRB and will ensure that the institution has a properly structured research committee. The University of Arizona Human Subjects Protection Program will be the IRB of record. Documentation of initial and ongoing reviews, submission of serious adverse event reports, study amendments and revisions, and consent form modifications will be required. This documentation is to be forwarded to:

• Consent Forms:

[name]

Clinical Research Coordinator

The University of Arizona Cancer Center – North Campus

Room 2111

[name]

[name]

• Regulatory Documents:

[name]

Lymphoma Program Regulatory Coordinator

The University of Arizona Cancer Center, Room 1955

[name]

[name]

13.A.2 Patient Information and Informed Consent

Written informed consent will be obtained for this study from all patients. The investigator or his/her staff will explain the nature of the study and the risks involved to each patient prior to his/her inclusion in the trial. The patient will also be informed that he/she is free to withdraw from the study at any time. Original, signed informed consent forms for patients registered from the University of Arizona Cancer Center will be kept at The University of Arizona Cancer Center, North Campus, room 2111.

13.B Registration Procedure

All ethical, regulatory, technical, and scientific approvals must be in place before study registrations will accepted. All patients will be registered centrally with the Clinical Research Coordinator based at [contact] prior to the initiation of treatment. The Clinical Research Coordinator will assign each patient a sequential number prior to registration. The fully signed informed consent must be presented and all inclusion and exclusion criteria will be reviewed with the registering investigator or designee. All source documentation needed to confirm eligibility must be available for this review. A second phone registration is required prior to the initiation of Zevalin® to confirm eligibility and dose of therapy.

13.C Study Records - Data Collection & Recording

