APPENDIX A

STUDY CALENDAR

4/1/2010

STUDY CALENDAR Page 1

					Ibritumomab Tiuxetan (Zevalin)			
Required Studies	Baseline	ESH	AP Treatm	ent		Regin	nen [∞]	
Visits (weeks or days)	Within28 days prior to C1, D1	Cycle 1 Day 1	Cycle 2 Day1	Cycle 2 Day 29	Day 1	Day 2,3,4,5	Day 7, 8, or 9	Day 35
PHYSICAL								
History / Physical / vital signs ^α	X		X	X	ΧП			
Height / Weight / BSA / PS	X		X	X	ΧП			
Disease Assessment	X			X				
Toxicity Assessment	X		X	X	ΧП			
LABORATORY								
CBC / differential / platelets	X		X	X	ΧП			\mathbf{X}^{Σ}
Serum Creatinine / BUN	X		X	X	ΧП			
AST/ ALT/ Alk. Phos/ T. Bilirubin^	X							
LDH	X							
BHCG [†]	X							
Beta 2- microglobulin	X							
Hepatitis B screen*	X							
Pathology Review [£]	X							
Bone marrow cytogenetics [¥]	X			X				
Bone marrow aspiration and Bx	X			X				
SCANS								
CT or PET Chest	X			X				
CT or PET Abdomen	X			X				
CT or PET Pelvis	X			X				
Gamma Scan						X≠		
TREATMENT								
ESHAP		X	X					
Rituximab 250 mg/m2					X		X	
Ibritumomab Tiuxetan Indium (¹¹¹ In Zevalin)					X			
Ibritumomab Tiuxetan Ytrium-90 (90Y Zevalin)							X	

- α Vital Signs consist of BP, temperature and pulse
- t Baseline for women of childbearing potential
- ¥ A scan is performed at 48-72 hours after 111In Zevalin. Another optional scan may be performed at 90-120 hours after 111In Zevalin.
- ∞ ¹¹¹In Zevalin is administered 4-6 weeks after completion of ESHAP.
- ٨ Required at Baseline and Encouraged to repeat as clinically indicated by Good Medical Practice.
- Encouraged by Good Medical Practice, but not required.
- ¥ Bone Marrow cytogenetics can be done at either Baseline or C2,D29, but must be done at least once.
- £ Pathology Review consists of a basic review of a pathology report. If possible submit: Representative H&E stained slides from the diagnostic biopsy, one representative paraffin block and one copy of the pathology report.
- Σ Starting Day 35 (+/- 7 days) a CBC w/ Diff and Platelet count should be done every week until nadir.
- Within 28 days prior to Rituximab & Zevalin administration..

STUDY CALENDAR Page 2

Required Studies	Restaging	Short-Term Follow-Up				Long-Term Follow-Up	Off-Study [#]
Visits (weeks or days)	3 mos post ⁹⁰ Y Zevalin	6 mos post Zevalin	12 mos post Zevalin	18 mos post Zevalin	24 mos post Zevalin	Follow-Up: Annually for 3 years [£]	Disease Progression or Removed from Study (within 4 weeks)
PHYSICAL							
History / physical / vital signs ^α	X	X	X	X	X	X	X

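### Section 8.B.5 calls for HBsAg testing of never-vaccinated, never-tested patients, but the only scheduled hepatitis B screen is marked optional, with no exception for them

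*Combined protocol and SAP*

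**What the plan says.** Three parts of the combined protocol and SAP deal with hepatitis B.

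- **Section 8.B.5** (rituximab toxicities) gives the testing instruction: "Patients who have never received vaccination for HBV, and have not had serologic testing for HBsAg, should be tested for surface antigen positivity". It also sets two safeguards. The first is monitoring: "Carriers of hepatitis B should be closely monitored for clinical and laboratory signs of active HBV infection". The second concerns patients with evidence of active liver disease or known HBV infection, who "should only receive rituximab if they have control of the infection and are adequately informed of the risks".
- **Section 5.A.4** (baseline laboratory tests) lists "Hepatitis B screen (encouraged by Good Medical Practice, but not required".
- **Appendix A** (study calendar, page 1) marks the hepatitis B screen at Baseline only, with the footnote "Encouraged by Good Medical Practice, but not required". Page 2 of the calendar has no hepatitis B row.

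For Day 1 of the Zevalin regimen, when rituximab is first given, 5.C.1 lists CBC with differential and platelets, BUN and creatinine. It adds: "The above mentioned tests and assessment are to be performed within 28 days of Rituximab & Zevalin administration". Section 13.B provides one later checkpoint: "A second phone registration is required prior to the initiation of Zevalin® to confirm eligibility and dose of therapy".

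**The concern.** Both safeguards in 8.B.5 work only if the carrier is known. For a patient with no vaccination and no earlier serology, the HBsAg test is the step that makes carriage known. Yet the two places from which a site would normally plan its screening visit, the baseline list and the calendar, say that the test may be left out, and they say so without qualification.

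What is at stake is patient safety. The protocol names the hazard itself: the heading of 8.B.5 refers to HBV reactivation with fulminant hepatitis, and the rituximab risk list in 6.B.2 includes reawakening of latent viruses. Every patient who goes on to the Zevalin regimen is scheduled for rituximab on Day 1 and again on Day 7, 8 or 9.

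**Working it through.** The plan states no figure on this point, so the check sets the sections side by side.

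**Step 1. What each provision asks for.**

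| Place | Who | Strength | When |
|---|---|---|---|
| 8.B.5, test | never vaccinated and never tested | should | not stated |
| 8.B.5, rituximab restriction | active liver disease or known HBV | should only | bears on the decision to give rituximab |
| 5.A.4 | all patients | encouraged, not required | baseline |
| Appendix A footnote | all patients | encouraged, not required | baseline |

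The opening line of 5.A makes the listed evaluations mandatory in the 28 days before Cycle 1 Day 1 unless otherwise specified. The hepatitis B screen is otherwise specified, so that rule does not make it compulsory. Neither 5.A.4 nor the footnote points to 8.B.5.

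**Step 2. Is a deadline implied?** Yes. The restriction governs whether rituximab is given, so the result is needed before the first infusion on Zevalin regimen Day 1. Section 8.B.5 does not write this down and attaches the test to no visit.

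**Step 3. Would anything else catch an untested carrier before rituximab?**

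- *Eligibility (4.A, 4.B).* No criterion mentions HBV. Section 4.B.8 excludes serious infection in the opinion of the investigator or sponsor, which presupposes that someone is aware of it.
- *Liver tests.* AST, ALT, alkaline phosphatase and bilirubin are required at baseline; afterwards, repeats are only encouraged as clinically indicated. Section 4.B.4 excludes bilirubin above 2.0 mg/dL, and the note in 4.A.12 requires bilirubin below 2.0 for progression to Zevalin. A carrier with normal values passes all of these.
- *Zevalin regimen Day 1 (5.C.1).* The listed blood tests include neither liver tests nor HBV serology.
- *Second registration (13.B).* It confirms eligibility and dose. Because HBV status is not an eligibility criterion, the call need not ask about it.

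**Result.** The gap is confined to patients who are never vaccinated, never tested, carriers, and unremarkable on liver tests, at a site that follows 5.A.4 and the calendar without also applying 8.B.5.

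**Step 4. Size.** The documents give no proportion never vaccinated and never tested, no carrier prevalence, and no expected number reaching rituximab out of the 52 evaluable patients planned. The number affected therefore cannot be computed, and any figure would be an outside assumption.

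**The case against.** The strongest reply is that the provisions can be read together. Section 5.A.4 sets a default for everyone, 8.B.5 adds a specific instruction for a subgroup, and a site is bound by the whole protocol. A site that applies 8.B.5 would test. The Amendment 3 log (Appendix L) also shows that the optional wording was put into 5.A.4 deliberately. This stands as far as it goes and limits the weight of the point. It does not remove it: two sites could each follow protocol text and handle the same untested patient differently.

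Four stronger readings might be inferred, and the documents do not support them.

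- *That 8.B.5 sets no time limit at all.* It names none, but the restriction on rituximab implies one.
- *That the second registration fails because it could come after rituximab.* Table 8 does say of rituximab "Give prior to 111 In Zevalin". However, 7.B and Appendix A treat rituximab as part of the Zevalin regimen, so the natural reading places the call before Day 1 rituximab. It fails as a backstop only because HBV is not an eligibility matter.
- *That the result must be in hand before Cycle 1 Day 1.* Section 6.A.4 says in general terms that glucocorticoids weaken the response to viral infection, but 8.B.5 restricts rituximab and sets no dosing rule for ESHAP in carriers. Baseline testing is sensible; a compulsory deadline before ESHAP would go beyond the protocol's own rule.
- *That calendar counts or elapsed time measure the risk.* With no cycle delay, and counting 4 to 6 weeks from the last ESHAP dose (Cycle 2 Day 4, study day 28 + 4 = 32), first rituximab falls on day 60 to 74, which is 59 to 73 days after Cycle 1 Day 1. Counted from the end of a 28-day second cycle (day 56), it falls on day 84 to 98, or 83 to 97 days. Neither interval says how likely the test is to be missed.

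**Conclusion.** The point holds as an unreconciled safety instruction. The protocol directs a test for a defined subgroup and then lists the only scheduled occasion for that test as optional for all, without cross-reference. A reader might call this a flat contradiction; it is not, because 8.B.5 says *should* and a specific instruction can sit beside a general default.

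The conclusion rests on two readings. The first is that sites plan screening mainly from 5.A.4 and the calendar. The second is that the Appendix A footnote belongs to the hepatitis B row: its marker did not survive text extraction, but its wording matches 5.A.4.

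The number of patients affected is unknown. There is no effect on the sample size, the error rates or the primary analysis. This is a cheap improvement for patient safety.

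**What to change.** In 5.A.4 and in the Appendix A footnote, replace the present qualifier with:

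> HBsAg testing is required for patients with no HBV vaccination and no prior HBsAg result (see 8.B.5), preferably on the baseline draw, with the result reviewed before the first rituximab infusion (Zevalin regimen Day 1) at the latest; encouraged for all others.

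No new visit, eligibility criterion or liver test is needed. The cost is a wording amendment in two places and one additional serology for each untested patient, whom 8.B.5 already says to test. The downside is that a carrier will occasionally be delayed or managed differently, which is the purpose of 8.B.5. A bare cross-reference from 5.A.4 and Appendix A to 8.B.5 would be lighter, but it would leave the test described as not required and the deadline unwritten.
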